7.3.2 Secondary endpoint analyses

7.3.2.1 Secondary PK endpoint analyses

The secondary PK endpoint $C_{min, 30-32}$ will be analyzed in the same way as the primary endpoints (see Section 7.3.1). However, only the mean ratio and CIs will be calculated and presented. No formal comparison to margins will be performed.

The secondary PK endpoint $t_{max, 30-32}$ will be analyzed in a descriptive manner only.

7.3.2.2 Secondary efficacy endpoint analyses

All secondary efficacy endpoint analyses will be based on the PPS and incomplete or missing data will be handled as described in Section 7.3.2.

The analysis of efficacy endpoints (see Section 2.1.3) will be based on asymptotic method.

The difference in proportions will be calculated as the difference between the observed proportions in each treatment group. Conficence intervals for the difference of proportions will be obtained using the Wald method, which is based on the asymptotically normal approximation to the distribution of the observed sample proportions.

The 90% and 95% CIs will be provided.

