	Starting at Week 14, the treatment regimen of the two arms will be: • Continuous Humira® arm: US-licensed Humira® (34 weeks) • Switching arm: BI 695501 (4 weeks, 2 injections)/US-licensed Humira® (4 weeks, 2 injections)/BI 695501 (10 weeks, 5 injections for primary endpoint + 16 weeks, 9 injections extension period; 26 weeks total) Patients will undergo intensive PK sampling between Weeks 12-14 (Visit 8, Visits 8a-d, and Visit 9) and 30-32 (Visit 17, Visits 17a-d, and Visit 18) to assess PK similarity between the two arms. After approximately 86 patients have had their Week 32 endpoint assessments and are PK evaluable, a blinded interim analysis with sample size re-assessment will be performed. Recruitment (for stage 2) will however not be stopped. The interim analysis will be performed in a blinded manner.							
Number of patients entered:	Initial enrollment into the run-in US-licensed Humira® arm: Approximately 240 patients will be entered.							
Number of patients on each treatment:	Patients will be randomized 1:1 into continuous US-licensed Humira® and switching arms at Week 14, leading to approximately 96 patients per arm, considering approximately 80% achieve PASI50 and a PK non-evaluable drop-out rate of approximately 10%-15%, to obtain approximately 86 PK evaluable patients per arm for the primary endpoint analysis.							
Diagnosis:	Moderate to severe chronic plaque psoriasis.							
Main in- and exclusion criteria	This trial will include male and female participants at least 18 years of age who have a diagnosis of moderate to severe chronic plaque psoriasis of at least 6 months duration prior to randomization, and which has been stable for the last 2 months with no changes in morphology or significant flares. Patients must be suitable for systemic treatment or phototherapy. Patients must have a PASI score \geq 12, Static Physician's Global Assessment of psoriasis (sPGA) \geq 3 at screening and at baseline, and a body surface area (BSA) involvement \geq 10%. Patients with prior exposure to any biologic therapy will be excluded from this trial.							
Test product(s):	BI 695501 solution in a pre-filled syringe							
dose:	40 mg every other week, starting at Week 14							
mode of administration:	Subcutaneous (s.c.) injection							
Comparator products:	US-licensed Humira® solution in a pre-filled syringe							
dose:	80 mg initial dose, followed by 40 mg every other week starting 1 week after initial dose							

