2. TRIAL OBJECTIVES AND ENDPOINTS

2.1 MAIN OBJECTIVES, PRIMARY AND SECONDARY ENDPOINTS

2.1.1 Main objectives

The primary objective of the trial is to assess the PK similarity between patients receiving US-licensed Humira[®] continuously vs those who switch between BI 695501 and US-licensed Humira[®], in patients with moderate-to-severe chronic plaque psoriasis.

The secondary objectives of this trial are to descriptively compare the safety, immunogenicity and efficacy profiles between patients receiving US-licensed Humira[®] continuously vs those who switch between BI 695501 and US-licensed Humira[®].

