7.3.1 Primary endpoint analyses

The analyses will be performed on the PKS and done 'as treated'.

The PK similarity of the two treatments (switching arm versus continuous Humira[®] arm) will be tested for the primary parameters $AUC_{\tau, 30-32}$ and $C_{max, 30-32}$ (see Section 2.1.2 for details).

Page 58 of 105

Proprietary confidential information © 2019 Boehringer Ingelheim International GmbH or one or more of its affiliated companies

The ratios of the means including their two-sided 90.2% CIs will be calculated. The confidence interval will be calculated according to Fiellers theorem [R12-1809]. As stated in [R12-1809, chapter 10.2.1], equivalence will be concluded if Fieller's 90.2% confidence interval for the ratio of means is included in the equivalence range 80.00% - 125.00% and

$$\frac{|\overline{Y}_R|}{\hat{\sigma}\sqrt{\frac{1}{n_R}}} > t_{1-\alpha,n_T+n_R-5}$$

which is equivalent to rejecting both null hypotheses. Thereby \bar{Y}_R refers to the LSMean of the reference treatment, $\hat{\sigma}$ is the residual standard deviation from the ANCOVA model (M1) below, n_T and n_R are the final sample sizes in the test and reference arm, respectively, and $\alpha = 4.9\%$.

The statistical model used for the analysis of $AUC_{\tau, 30-32}$ and $C_{max, 30-32}$ will be an analysis of covariance (ANCOVA) model on the original scale. This model will include effects accounting for:

- Treatment (switching arm versus continuously Humira® arm)
- Logarithm of rPASI, where rPASI is the ratio of PASI at Week 14 and PASI at Week 1 (continuous value)
- Weight at Week 14 (continuous value)
- Stage, where stage represents the two parts of the study prior to and after the blinded sample size reassessment (categorical, 1 or 2)
- AUC_{τ . 12-14} or C_{max. 12-14} (continuous value)

as a source of variation. As the measurements at Week 14 will be prior to randomization and all patients will have received the same treatment with the reference treatment only, the covariates listed above are all considered adequate baseline values.

All effects will be considered as fixed. The model is described by the following equation: (M1) response (AUC $_{\tau}$ or C $_{max}$) = overall mean + treatment effect + log(rPASI) + weight at Week 14 + stage + AUC $_{\tau}$, 12-14 or C $_{max}$, 12-14 + random error.

where the random errors are assumed to be independent and normally distributed with zero mean and variance σ_k^2 where k is either test or reference treatment.

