7.6.2 Efficacy data

For the analysis of secondary efficacy endpoints, missing PASI75 and sPGA data will be imputed using the multiple imputation (MI) method.

However, all patients who discontinue treatment, are lost-to-follow-up or have any severe violation related to any therapy that may significantly impact efficacy assessment (Table 4.2.2.1: 1) prior to the secondary efficacy endpoints assessment will be considered as a non-responder. This is referred to as 'NRI'.

For more details refer to the TSAP.

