7.7 RANDOMISATION

On Day 1, all patients meeting the eligibility criteria will be entered and receive Humira[®] during the run-in phase. At the beginning of Week 14, patients with at least a partial response (PASI50) will be randomized at 1:1 to either receive Humira[®] until Week 48 or alternatively receive BI 695501 and Humira[®] until Week 48. Patients not achieving at least a PASI50 response at Week 14 will be considered as non-responders and will be discontinued from the trial. At Week 14, the randomization will be stratified by the level of their Week 14 response (≥ PASI50 to < PASI75 and ≥ PASI75). Access to the randomization code will be controlled and documented. All persons directly involved in the conduct and analysis of the trial will have no access to the treatment allocation prior to final database lock except for unblinded qualified staff who will prepare and administer trial medication. The block sizes of the randomization will be documented in the CTR.

Page 64 of 105

Proprietary confidential information © 2019 Boehringer Ingelheim International GmbH or one or more of its affiliated companies

8. INFORMED CONSENT, TRIAL RECORDS, DATA PROTECTION, PUBLICATION POLICY, AND ADMINISTRATIVE STRUCTURE

The trial will be carried out in compliance with the protocol, the ethical principles laid down in the Declaration of Helsinki, in accordance with the ICH Harmonized Tripartite Guideline for GCP, relevant BI SOPs, the EU regulation 536/2014, and other relevant regulations.

Standard medical care (prophylactic, diagnostic and therapeutic procedures) remains the responsibility of the treating physician of the patient.

The investigator will inform the sponsor immediately of any urgent safety measures taken to protect the trial patients against any immediate hazard, as well as of any serious breaches of the protocol or of ICH GCP.

The BI transparency and publication policy can be found on the following web page: trials.boehringer-ingelheim.com. The rights of the Investigator and of the sponsor with regard to publication of the results of this trial are described in the Investigator contract.

The certificate of insurance cover is made available to the Investigator and the patients, and is stored in the ISF.

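### Week 32 PASI75 and sPGA ≤ 1 are compared with an unstratified Wald interval although randomization is stratified by Week 14 PASI response; if that stratum is prognostic, the intervals are wider than the design supports

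*Protocol*

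**What the plan says.** Section 7.3.2.2 names both the estimator and the interval for the two secondary efficacy endpoints, PASI75 and sPGA ≤ 1 at Week 32. On the estimator: "The difference in proportions will be calculated as the difference between the observed proportions in each treatment group". On the interval, it is obtained "using the Wald method, which is based on the asymptotically normal approximation to the distribution of the observed sample proportions". Both 90% and 95% intervals are to be given, on the Per-Protocol Set. No stratum term or weighting appears.

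Section 7.7 (and likewise 4.1.3) says: "At Week 14, the randomization will be stratified by the level of their Week 14 response". The two strata are PASI50 up to but not including PASI75, and PASI75 or better.

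The primary pharmacokinetic model in Section 7.3.1 does adjust for the continuous form of this factor: "Logarithm of rPASI, where rPASI is the ratio of PASI at Week 14 and PASI at Week 1".

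Section 7.6.2 adds that "missing PASI75 and sPGA data will be imputed using the multiple imputation (MI) method", with treatment discontinuations, losses to follow-up and certain therapy violations counted as non-response. The role of the comparison is set in Section 2.1.1: "The secondary objectives of this trial are to descriptively compare the safety, immunogenicity and efficacy profiles".

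**The concern.** The stratum is the PASI75 endpoint itself, measured 18 weeks earlier in the same patients, and it is a closely related measure for sPGA ≤ 1. It is therefore likely to predict Week 32 response. Stratified randomization balances the arms on it, which lowers the true sampling variance of the difference between arms. A Wald variance built from the overall arm proportions takes no account of that balance, so it overstates the uncertainty.

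The efficacy comparison has no test and no margin, so its result is an estimate with its intervals. Intervals that are too wide leave larger differences between switching and continuous treatment looking compatible with the data than the design requires. The protocol uses Week 14 PASI response to randomize and to adjust the pharmacokinetic model, but not in the analysis of PASI and sPGA.

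This is not a detail left to the statistical analysis plan, because the protocol itself fixes the unstratified method.

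**Working it through.** **Inputs from the protocol.** The Synopsis gives about 240 patients entered, about 80% reaching PASI50, and 1:1 allocation, "leading to approximately 96 patients per arm". This reproduces: 240 × 0.80 / 2 = 96. The 86 pharmacokinetically evaluable per arm also reproduces at 10% loss: 96 × 0.90 = 86.4. The size of the Per-Protocol Set is not stated, so 96 per arm is used below.

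**Inputs that are assumptions.** The protocol states neither the share of patients in each stratum nor any Week 32 response rate. Let w be the share in the PASI75-or-better stratum, and p1 and p0 the Week 32 response in the upper and lower strata, equal in both arms.

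**Formulas.** With p = w·p1 + (1−w)·p0 and n per arm:

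- Crude Wald variance of the difference: 2·p(1−p)/n
- Stratified variance: 2·[w·p1(1−p1) + (1−w)·p0(1−p0)]/n
- Excess of crude over stratified: 2·w(1−w)(p1−p0)²/n

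The excess is zero when the stratum is not prognostic and positive otherwise.

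**One case in full: w = 0.70, 90% versus 40%.** p = 0.63 + 0.12 = 0.75, so p(1−p) = 0.1875. Within strata: 0.70 × 0.09 + 0.30 × 0.24 = 0.1350. The difference is 0.0525 = 0.21 × 0.50², as the formula requires. The standard error ratio is √(0.1350/0.1875) = 0.849, which is 15.1% smaller. At n = 96 the 95% half-width falls from 1.96 × √(2 × 0.1875/96) = 12.2 points to 1.96 × √(2 × 0.1350/96) = 10.4 points. The 90% half-width falls from 10.3 to 8.7.

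**Other cases.** Coverage is for a nominal 95% interval, simulated with 200,000 trials, 96 per arm, arms balanced within strata and no treatment difference. The stratified method is Mantel-Haenszel with the Sato standard error.

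| w | p1 / p0 | Crude p(1−p) | Within-stratum | SE reduction | Coverage, crude | Coverage, stratified |
|---|---|---|---|---|---|---|
| 0.68 | 95% / 30% | 0.1914 | 0.0995 | 27.9% | – | – |
| 0.60 | 95% / 30% | 0.2139 | 0.1125 | 27.5% | 99.2% | 94.8% |
| 0.70 | 90% / 40% | 0.1875 | 0.1350 | 15.1% | 97.8% | 94.8% |
| 0.85 | 85% / 50% | 0.1615 | 0.1459 | 5.0% | 96.0% | 94.8% |
| 0.70 | 85% / 60% | 0.1744 | 0.1613 | 3.8% | 95.7% | 94.8% |
| 0.80 | 85% / 70% | 0.1476 | 0.1440 | 1.2% | – | – |
| 0.70 | 80% / 70% | 0.1771 | 0.1750 | 0.6% | 94.9% | 94.7% |

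The 27.9% and 5.0% rows are the extremes of a grid with w from 0.60 to 0.85, p1 from 85% to 95% and p0 from 30% to 50%. A repeat of the simulation agreed to within 0.1 point.

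For 85% versus 60% (w = 0.70) the 95% half-width moves only from 11.8 to 11.4 points. At 86 per arm all half-widths grow by √(96/86) = 1.06, and the ratios do not change.

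**The case against.** The strongest reply is that nothing here is wrong. The crude risk difference is unbiased, its interval errs only towards caution, and no decision depends on its width. Section 3.2 says the clinical efficacy endpoints are not sensitive enough to show an effect of immunogenicity, and pharmacokinetics carries the formal equivalence test. That also weakens the comparison with the adjusted pharmacokinetic model. All of this stands, and it limits the importance of the point.

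The size is open to challenge too. The 5.0% to 27.9% range needs a gap of at least 35 points between strata. Everyone randomized has reached PASI50 and stays on active treatment, so the lower stratum may catch up. Counting discontinuations as non-response may narrow the gap further. With a gap of 10 to 15 points the gain is negligible. This stands: the larger figures are possibilities, not expectations.

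Exclusions from the Per-Protocol Set may disturb the balance between arms. With an assumed 12% random exclusion, crude coverage at 90% versus 40% falls from 97.8% to 97.4%, so the effect remains. The stratified interval is also slightly below nominal at the 90% level: 89.6% to 89.8% for Mantel-Haenszel with Sato, and as low as 88.9% for a plain stratum-size-weighted version. That is acceptable, but it is a small cost.

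Finally, parts of the protocol are not in the public text, and a supportive adjusted analysis there cannot be ruled out. It would not change the main estimate that Section 7.3.2.2 fixes.

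**Conclusion.** The concern holds in its conditional form. If Week 14 PASI response predicts Week 32 response, the planned 90% and 95% intervals over-cover and are wider than the stratified design supports. The condition is plausible because stratum and endpoint share the PASI75 cut-off, but the protocol offers no figures to confirm it. On assumed rates, the reduction in standard error runs from 0.6% for a 10-point gap, through 3.8% for a 25-point gap, to 27.9% at the extreme of the range tried. There is no bias, no margin is affected, and the primary pharmacokinetic conclusion does not change. This is an optional gain in precision for a descriptive secondary objective.

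**What to change.** In Section 7.3.2.2, make the main efficacy estimate a Mantel-Haenszel risk difference weighted over the two Week 14 PASI randomization strata, with a stratified standard error such as Sato's. Compute the estimate and standard error in each imputed data set, pool them by Rubin's rules, and report the 90% and 95% intervals as already planned. Keep the crude difference as supportive description.

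The cost is one paragraph in the protocol and matching wording in the statistical analysis plan. No new data, visits or patients are needed, because the stratum is already recorded for randomization. If the stratum turns out not to be prognostic, the two intervals are practically the same and almost nothing is lost.

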7.3.2.3 Secondary immunogenicity endpoint analyses

All secondary immunogenicity endpoint analyses will be based on the TS. All secondary immunogenicity endpoints will be summarized descriptively.

For analysis of the secondary endpoint dedicated to safety, see Section 7.3.4.

Page 60 of 105

Proprietary confidential information © 2019 Boehringer Ingelheim International GmbH or one or more of its affiliated companies

7.3.4 Safety analyses

The safety analyses will be descriptive in nature. The analyses will be performed based on the TS and RTS.

The proportion of patients with drug-related AEs during the treatment phase will be analyzed as a secondary safety endpoint.

For the proportion of patients with AESIs, risk ratios and 95% CIs will be provided in addition.

Adverse events will be coded using the Medical Dictionary for Regulatory Activities (MedDRA) coding dictionary. Standard BI summary tables and listings will be produced.

Safety measurements (such as ECG, vital signs or laboratory parameters) and AEs as well as local tolerability assessments will be assigned to treatments, based on the actual treatment at the time of the measurement, or on the recorded time of AE onset (concept of treatment emergent AEs). That is, measurements and AEs recorded prior to first trial drug administration will be assigned to 'screening'; those between the first Humira[®] intake and up to the drug administration on Week 14 will be assigned to "run-in" period. All AEs occurring between start of treatment and end of the REP will be considered 'treatment-emergent' with respect to the randomized treatment arm. Adverse events that start before first drug intake and deteriorate under treatment will also be considered as 'treatment-emergent' (with respect to the randomized treatment arm).

Laboratory assessments after the first dose of trial medication up to a period of 10 weeks after the last dose of the trial medication will be assigned to the treatment phase for evaluation. Laboratory values will be compared to their reference ranges and frequency tables by visit will be provided for the number of patients within and outside the reference range.

Vital signs, physical examinations, 12-lead ECG, or other safety-relevant data observed at screening, baseline, during the course of the trial and at the end-of-trial evaluation will be assessed with regard to possible changes compared to findings before start of treatment.

7.3.5 Pharmacokinetic and pharmacodynamic analyses

The PK parameters listed in Sections 2.1.2, 2.1.3, 2.1.4 for patients in the switching arm and in the US-licensed Humira[®]-continuous arm will be calculated using non-compartmental methods according to the relevant SOP of the sponsor and as described in the TSAP.

PKS will be used for the statistical analysis of PK parameters. Plasma concentrations will be analyzed descriptively for all patients in the run-in treated set (RTS). Moreover, PK parameters will be also descriptively analyzed for patients in the RTS.

Only concentration values within the validated concentration range and actual sampling times will be used for the calculation of PK parameters. Concentrations used in the PK calculations will be in the same format provided in the bioanalytical report, that is, to the same precision of decimal places or significant figures as provided in the bioanalytical report.

Clinical Trial Protocol

Page 61 of 105

Proprietary confidential information © 2019 Boehringer Ingelheim International GmbH or one or more of its affiliated companies

If a measured level for a given PK sample is BLQ then 1/2 LLOQ of the bioanalytical assay $(0.0125 \ \mu g/mL)$ will be used for the parameter calculations. For samples taken at baseline (visit 2) BLQ values will not be replaced by 1/2 LLOQ.

If all plasma concentrations of an intensive PK interval (week 12-14 and/or week 30-32) will be replaced by $\frac{1}{2}$ LLOQ, both C_{max} and C_{min} of the respective dosing interval will equal $\frac{1}{2}$ LLOQ. The corresponding t_{max} and t_{min} will be the actual time of the first plasma sample in this dosing interval.

Both analyte plasma concentrations and PK parameters for the switching arm and in the US-licensed Humira[®]-continuous arm will be listed and presented graphically as appropriate.

At least the following descriptive statistics will be calculated for plasma concentrations as well as for all PK parameters: N, arithmetic mean, standard deviation, minimum, median, maximum, Q1, Q3 (Q1 and Q3 only for PK parameters), arithmetic coefficient of variation (CV), geometric mean, and geometric CV. The descriptive statistics of PK parameters will be calculated using the individual values with the number of decimal places as provided by the evaluation program. Then, the individual PK values as well as the descriptive statistics will be reported with three significant digits in the CTR.

For the statistical analysis of the PK endpoints please refer to Section 7.3.1.

7.4 INTERIM ANALYSES

7.4.1 Blinded review of sample size

The blinded, pooled $AUC_{\tau, 30-32}$ or $C_{max, 30-32}$ will be monitored to verify the sample size assumptions.

Due to the uncertainty about the PK variability, a sample size re-assessment procedure as described in Friede and Kieser (P04-05360) and Golkowski et al (R16-4933) has been considered for this study. The initially planned total sample size is 170 PK evaluable patients (i.e., patients in the PKS and all necessary covariates are available). This is also set to be the minimum sample size for the trial.

For this study a maximum sample size to be recruited is set to 350. Taking into account the drop-out rates as described above this translates to a maximum of approximately 246 PK evaluable patients at Week 32.

After (approximately) 86 patients have had their Week 32 primary endpoints assessment and are PK evaluable the variability of $AUC_{\tau, 30-32}$ and $C_{max, 30-32}$ will be re-estimated based on the data of those 86 patients. This adequately allows the determination of the variability relevant for sample size (re-)calculation, which is in line with the primary endpoint analysis strategy. In order to mirror the primary endpoint analysis strategy the variability will be estimated after

Page 62 of 105

Proprietary confidential information © 2019 Boehringer Ingelheim International GmbH or one or more of its affiliated companies

stage 1 as the residual variance from the model as stated in Section 7.3.1 but, due to the blinded assessment, without the covariates 'Treatment' and 'Stage'.

More details will be specified in the TSAP. In addition, the TSAP will provide justification which demonstrates that the overall type I error is maintained.

No formal statistical testing for efficacy will be performed.

